7.7 EXTENT OF EXPOSURE

Descriptive statistics are planned for this section of the report, by fasting state and overall for the FE part. For the SRD part a listing will be sufficient.

7.8 SAFETY ANALYSIS

All safety analyses will be performed on the TS.

7.8.1 Adverse events

AEs will be coded with the most recent version of MedDRA.

The analyses of AEs will be descriptive in nature. All analyses of AEs will be based on the number of subjects with AEs and not on the number of AEs.

For analysis, multiple AE occurrence data on the electronic case report form (eCRF) will be collapsed into an AE event provided that all of the following applies:

- All AE attributes are identical (LLT, intensity, action taken, therapy required, seriousness, reason for seriousness, relationship, outcome, AESI)
- The occurrences were time-overlapping or time-adjacent (time-adjacency of two occurrences is given if the second occurrence started at most 1 hour after the first occurrence ended).

For further details on summarization of AE data, please refer to "Analysis and presentation of adverse event data from Clinical Trials" (7) and "Handling of missing and incomplete AE dates" (3).

The analysis of AEs will be based on the concept of treatment emergent AEs. That means that all AEs will be assigned to the screening or treatment phases as defined in [Section 6.1](#). AEs will be analysed based on actual treatments, as defined in [Table 6.1: 1](#).

An overall summary of AEs will be presented. This overall summary will comprise summary statistics for the class of other significant AEs according to ICH E3 (8) and for the class of AESIs.

CTP: Hepatic injury

A hepatic injury is defined by the following alterations of hepatic laboratory parameters::

- *An elevation of AST (aspartate transaminase) and/or ALT (alanine transaminase) ≥ 3 -fold ULN combined with an elevation of total bilirubin ≥ 2 -fold ULN measured in the same blood sample, or*
- *Aminotransferase (ALT, and/or AST) elevations ≥ 10 fold ULN*

The investigator had to classify on the eCRF whether an observed AE was an AESI or not.

According to ICH E3 (8), AEs classified as 'other significant' need to be reported and will include those non-serious and non-significant AEs

- (i) which are marked haematological or other lab abnormalities, or
- (ii) which were reported with 'action taken = discontinuation' or 'action taken = reduced', or
- (iii) which lead to significant concomitant therapy as identified by the Clinical Monitor/Investigator at a Medical Quality Review Meeting.

The frequency of subjects with AEs will be summarised by treatment, primary system organ class and preferred term. AEs which were considered by the investigator to be drug related will be summarised separately. Separate tables will also be provided for subjects with SAEs, subjects with AESIs and subjects with other significant AEs (according to ICH E3 (8)). AEs will also be summarized by maximum intensity.

The system organ classes will be sorted by total frequency, preferred terms will be sorted by total frequency (within system organ class).

For disclosure of AE data on ClinicalTrials.gov, the frequency of subjects with non-serious AEs occurring with an incidence of greater than 5 % (in preferred terms) will be summarised by treatment, primary system organ class and preferred term. The frequency of subjects with SAEs will also be summarised.

For disclosure of AE data in the EudraCT register, the frequency of AEs, the frequency of non-serious AEs with an incidence of greater than 5 % (in preferred terms) and the frequency of SAEs will be summarised.

For support of lay summaries, the frequency of subjects with drug-related SAEs will be summarised by treatment, primary system organ class and preferred term.

7.8.2 Laboratory data

The analyses of laboratory data will be descriptive in nature and will be based on BI standard "Display and Analysis of Laboratory Data" ([9](#)).

Analyses will be based on normalised values, which means transforming to a standard unit and a standard reference range.

Descriptive statistics of laboratory values over time and for the difference from baseline (see [Section 6.7](#)) will be provided. Frequency tables of changes between baseline and last value on treatment with respect to the reference range will be presented.

Possibly clinically significant abnormal laboratory values are only those identified either in the Investigator's comments on the eCRF or at the RPM at the latest. It is the Investigator's responsibility to decide whether a lab value is clinically significant abnormal or not. Standard or project-specific rules for flagging clinically significant values will not be applied in this study.

Clinically relevant findings in laboratory data will be reported as AEs and will be analysed as part of AE analysis.

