## FLOW CHART

Single rising dose (SRD) part:

Visit	Day	Planned time (relative to drug administration) [h:min]	Approximate clock time of actual day [h:min]	Event and comment	Safety laboratory	PK blood 	12-lead ECG	Continuous ECG monitoring	Vital signs (BP, PR)	Questioning for AEs and concomitant therapy 
1	-28 to -1			Screening (SCR) 	x					
2	-3 to -1	-72:00 to -24:00	08:00	Ambulatory visit	x 					x
	1	-1:30	06:30	Admission to trial site						
		-0:30	07:30	Allocation to treatment 	x 	x 				
		0:00	08:00	Drug administration						
		0:10	08:10			x				
		0:20	08:20			x				
		0:30	08:30			x				
		0:45	08:45			x				
		1:00	09:00			x 				
		1:30	09:30			x				
		2:00	10:00	240 mL fluid intake		x				
		3:00	11:00			x				
		4:00	12:00	240 mL fluid intake, thereafter lunch 	x	x				
		6:00	14:00			x				
		8:00	16:00	Snack (voluntary) 		x				
		10:00	18:00	Dinner 		x				
		12:00	20:00			x				
	2	24:00	08:00			x	x			
		34:00	18:00			x				
	3	48:00	08:00	Breakfast (voluntary)  , discharge from trial site	x	x				
	4	72:00	08:00	Ambulatory visit		x				
	5	96:00	08:00	Ambulatory visit	x	x				
	6	120:00	08:00	Ambulatory visit		x				
3	7 to 11			End of trial (EoT) examination 	x				x	x

1. Subject must be informed and written informed consent obtained prior to starting any screening procedures. Screening procedures include physical examination, check of vital signs, ECG, safety laboratory (including drug screening), demographics (including determination of body height and weight, smoking status and alcohol history), relevant medical history, concomitant therapy and review of inclusion/exclusion criteria.
2. The time is approximate; procedures are to be performed and completed within the 3 h prior to drug administration. Allocation to treatment may be performed at any time following enrolment but must be completed prior to (first) drug administration.
3. If several actions are indicated at the same time, the intake of meals will be the last action.
4. At the end of trial visit the EoT examination includes physical examination, body weight, vital signs, ECG, safety laboratory, recording of AEs, and concomitant therapies.
5. Only urine drug screening and alcohol breath test will be done at this time.

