#### **1.2.6 Residual Effect Period**

At the projected therapeutic dose, human effective half-life of BI 764122 is predicted to be 3.3 h [[n00264108](#)]. Due to the assumed TMDD, this value might be substantially exceeded. With reference to the half-life in female Cynomolgus monkey after intravenous ( $20.8 \pm 2.5$  h) and oral ( $26.5 \pm 7.2$  h) application (see [Table 1.2.3: 1](#)), the pharmacokinetic residual effect period is conservatively estimated to range from 5 to 7 days.

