##### 3.1.1 Single rising dose (SRD) part

The SRD part is designed as single-blind, partially randomised and placebo-controlled within parallel (sequential) DGs.

It is planned to include a total of 64 healthy male subjects in the SRD part. The subjects will be assigned to 8 groups consisting of 8 subjects per group; the groups will be dosed sequentially (see [Table 3.1: 1](#)). The investigator (after consultation with the sponsor) is allowed to alter the scheduled DGs (e.g., add low and/or intermediate DGs) on the basis of experience gained during the study (for instance, based on safety and/or preliminary PK data), provided the planned and approved highest dose is not exceeded. Thus, the actual number of subjects entered in the SRD part may be more than 64 but is not to exceed 80. Such changes, which are based on preliminary PK data, may be implemented via non-substantial CTP amendments. Changes, based on safety findings, will be implemented only via substantial CTP amendments.

Within each DG, 6 subjects will receive BI 764122 and 2 will receive placebo. Only one dose is tested within each DG. For safety reasons, each DG will consist of 3 cohorts. The trial medication will be administered in the following order:

- Cohort 1 (fixed order): the 1st subject on active treatment and the 2nd subject on placebo (in total 2 subjects)
- Cohort 2 (fixed order): 2 subjects on active treatment (in total 2 subjects)
- Cohort 3 (randomised): 3 subjects on active treatment and 1 subject on placebo (in total 4 subjects)

Between first drug administrations in Cohort 1 and 2, there will be a time interval of at least 24 hours which is expected to cover the peak exposure of BI 764122. If BI 764122 was safe and well tolerated in Cohort 1, the study will continue with Cohort 2. The 2 subjects of Cohort 2 will be dosed at least 1 hour apart. If BI 764122 was still safe and well tolerated in all subjects of Cohort 1 and 2, the study will proceed at least 24 hours after the first drug administration in Cohort 2 with the 4 subjects of Cohort 3, who will be dosed at least 15 minutes apart.

The DGs to be evaluated are outlined in [Table 3.1: 1](#) below.

Table 3.1: 1

Dose groups (DGs)

DG	1	2	3	4	5	6	7	8
Dose (mg)	4	12	25	50	100	200	300	400
Number of subjects	8	8	8	8	8	8	8	8
Subjects receiving placebo	2	2	2	2	2	2	2	2
Subjects receiving BI 764122	6	6	6	6	6	6	6	6

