#### **5.2.3 Safety laboratory parameters**

For the assessment of laboratory parameters, blood and urine samples will be collected by the trial site at the times indicated in the [Flow Chart](#) after the subjects have fasted for at least 10 h. For retests, at the discretion of the investigator or designee, overnight fasting is not required. The parameters that will be determined are listed in [Tables 5.2.3: 1](#) and [5.2.3: 2](#). Reference ranges will be provided in the ISF, Section 10.

Manual differential white blood cell count will be performed if there is an abnormality detected with the automatic blood cell count. Urine microscopic examinations will be performed in addition to urinalysis (Stix) in order to correctly evaluate possible abnormalities detected at the urinalysis (Stix)

Table 5.2.3: 1

Routine laboratory tests for SRD and FE part

Functional lab group	BI test name [comment/abbreviation]	SCR/ EoT	Day -3 to -1	Day 1, 4 h post	Day 2, 24 h post	Day 3, 48 h post	Day 5, 96 h post
Haematology	Haematocrit Haemoglobin Red blood cell count (erythrocytes), absol. Reticulocytes, absol. White blood cells (leucocytes), absol. Platelet count (thrombocytes), absol.	X X X X X X	X X X X X X	X X X X X X	X X X X X X	X X X X X X	X X X X X X
Automatic WBC differential, relative	Neutrophils/ leukocytes; eosinophils/ leukocytes; basophils/ leukocytes; monocytes/ leukocytes; lymphocytes/ leukocytes	X	X	X	X	X	X
Automatic WBC differential, absolute	Neutrophil, absol.; eosinophils, absol.; basophils, absol.; monocytes, absol.; lymphocytes, absol.	X	X	X	X	X	X
Manual differential WBC (if automatic differential WBC is abnormal) 	Neutrophils/ leukocytes; eosinophils/ leukocytes; basophils/ leukocytes; monocytes/ leukocytes; lymphocytes/ leukocytes Neutrophil, absol.; eosinophils, absol.; basophils, absol.; monocytes, absol.; lymphocytes, absol.	X 					
Coagulation	Activated partial thromboplastin time Prothrombin time – INR (International Normalization Ratio) Fibrinogen	X X X	X X X	X X X	X X X	-- -- --	-- -- --
Enzymes	AST [aspartate transaminase] /GOT, SGOT ALT [alanine transaminase] /GPT, SGPT Alkaline phosphatase Gamma-glutamyl transferase Creatine kinase [CK] Creatine kinase Isoenzyme MB [only if CK is elevated] Lactic dehydrogenase Lipase Amylase	X X X X X X X X X	X X X X X X X X X	X X X X X X X X X	X X X X X X X X X	X X X X X X X X X	X X X X X X X X X
Hormones 	Thyroid stimulating hormone	X	--	--	--	--	--

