#### **6.2.2 Treatment periods**

##### SRD part:

Each subject will receive one dose of trial medication (BI 764122 or placebo) at Visit 2.

Trial medication will be taken orally by each subject under direct supervision of the investigator or designee. Details on treatments and procedures of administration are described in [Section 4.1.4](#).

Proprietary confidential information © 2019 Boehringer Ingelheim International GmbH or one or more of its affiliated companies

Study participants will be admitted to the trial site in the morning of Day 1 and kept under close medical surveillance for at least 48 h following drug administration. The subjects will then be allowed to leave the trial site after formal assessment and confirmation of their fitness by the investigator or designee. On all other study days, subjects will be treated in an ambulatory fashion.

For details on time points, and procedures for collection of plasma samples for PK analysis, see [Flow Chart](#) and [Section 5.3.2](#).

The safety measurements performed during the treatment period are specified in [Section 5.3](#) of this protocol and in the [Flow Chart](#). For details on times of all other trial procedures, see [Flow Chart](#). AEs and concomitant therapy will be assessed continuously from screening until the end of trial examination.

FE part:

Each subject is expected to participate in two treatment periods. Treatment periods will be separated by at least 7 days between drug administrations.

Trial medication will be taken orally by each subject under direct supervision of the investigator or his/ her designee. Details on treatments and procedures of administration are described in [Section 4.1.4](#).

In the morning of Day 1 of each treatment period, participants will be admitted to the trial site and kept under close medical surveillance for at least 24 hours following drug administration. Subjects will then be allowed to leave the trial site after formal assessment and confirmation of their fitness. On all other study days, the study will be performed in an ambulatory fashion.

For details on time points and procedures for collection of plasma samples for PK analysis, see [Flow Chart](#) and [Section 5.3.2](#).

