6. GENERAL ANALYSIS DEFINITIONS

6.1 TREATMENTS

For basic study information on treatments to be administered, assignments of dose groups, and selection of doses, cf. Section 4 of the CTP.

Subjects were planned to be treated with

SRD part:

- either a single dose of 4, 12, 25, 50, 100, 200, 300 or 400 mg of BI 764122 (test treatments)
or
- a single dose of placebo (reference treatment)

All placebo subjects will be analysed in one pooled placebo group (i.e. no distinction between dose groups will be made for placebo subjects).

FE part:

- single dose of 50 mg BI 764122 in fed state (test treatment T) and in fasted state (reference treatment R) with a wash-out period of at least 7 days between treatments

Subjects will randomly be assigned to the treatment sequence (T-R) or (R-T).

For statistical analysis of AEs, safety laboratory data, vital signs and ECG, the following analysis phases are defined for each subject:

Table 6.1: 1 Flow chart of analysis phases for statistical analyses of AEs, safety laboratory data, ECG and vital signs

SRD part:

Study analysis phase	Label	Start (inclusive)	End (exclusive)
Screening	Screening	Date of informed consent	Date/time of first administration of study drug
On-treatment	Pbo, 4 mg BI, 12 mg BI, 25 mg BI, 50 mg BI, 100 mg BI, 200 mg BI, 300 mg BI or 400 mg BI respectively	Date/time of first administration of study drug	Date/time of last administration of study drug + 7 * 24 h (i.e., REP of 7 days) or 0:00 AM on day after subject's trial termination date whatever occurs earlier
Follow-up	F/U Pbo, F/U 4 mg BI, F/U 12 mg BI, F/U 25 mg BI, F/U 50 mg BI, F/U 100 mg BI, F/U 200 mg BI, F/U 300 mg BI or F/U 400 mg BI respectively	Date/time of last administration of study drug + 7 * 24 h	0:00 AM on day after subject's trial completion date

FE part:

Study analysis phase	Label	Start (inclusive)	End (exclusive)
Screening	Screening	Date of informed consent	Date/time of first administration of study drug
On-treatment	BI fed, BI fasted	Date/time of first administration of study drug of respective treatment	Date/time of administration of study drug in next period or date/time of administration of study drug + 7 * 24 h (i.e., REP of 7 days) or 0:00 AM on day after subject's trial completion date whatever occurs earlier
Follow-up	F/U BI	Date/time of administration of study drug + 7 * 24 h	Date/time of second administration of study drug or 0:00 AM on day after subject's trial completion date

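### Laboratory shift tables use only the last on-treatment value, so no specified table counts subjects who were out of range earlier and recovered

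*SAP*

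**What the plan says.** SAP 7.8.2 plans by-time descriptive statistics of laboratory values and of differences from baseline, and one categorical comparison with the reference range: "Frequency tables of changes between baseline and last value on treatment with respect to the reference range will be presented". The same section leaves clinical significance to the investigator's comments or the report planning meeting, and rules out standard or project-specific flagging rules.

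What counts as on treatment comes from SAP Table 6.1: 1. In the single rising dose (SRD) part the phase ends at "Date/time of last administration of study drug + 7 * 24 h (i.e., REP of 7 days"), end exclusive, or at trial termination if that is earlier. In the food effect (FE) part it ends at "Date/time of administration of study drug in next period or date/time of administration of study drug + 7 * 24 h" or at trial completion, whichever comes first.

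Protocol Table 5.2.3: 1, headed for both parts, schedules post-dose samples at 4, 24, 48 and 96 h. The coagulation panel ("Activated partial thromboplastin time", prothrombin time/INR, fibrinogen) is taken at 4 and 24 h but not at 48 or 96 h. The EoT visit falls on Day 7 to 11 and includes a further sample: "At the end of trial visit the EoT examination includes physical examination, body weight, vital signs, ECG, safety laboratory".

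Dosing in the SRD part is single: "Each subject will receive one dose of trial medication (BI 764122 or placebo) at Visit 2". On group size, Protocol 3.1.1 says: "Within each DG, 6 subjects will receive BI 764122 and 2 will receive placebo".

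**The concern.** After a single dose, a laboratory change may appear at 4, 24 or 48 h and resolve. A table that pairs baseline with the last on-treatment value cannot show that course; the subject is counted as unchanged. Other parts of the same SAP do not work this way. The ECG categories in SAP 5.3.2 use maximum on-treatment values, the ECG notable findings there apply at any time on treatment, and adverse events are summarised by maximum intensity (SAP 7.8.1). No reason is given for treating laboratory data differently.

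The laboratory data are not peripheral. Protocol 1.4.3.5 gives safety laboratory monitoring a particular focus on glycaemic control, liver and haematology, and Protocol 1.3.2 bases the exposure limit partly on ALT findings in dogs. The stake is a clear, objective comparison of out-of-range frequencies between dose groups and placebo in the trial report.

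**Working it through.** The plan states no figure to reproduce. The check is on timing, then on counting.

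**Inputs.** Post-dose samples at 4, 24, 48 and 96 h, with coagulation at 4 and 24 h only (Protocol Table 5.2.3: 1). EoT on Day 7 to 11 (Flow Chart). On-treatment end at 7 × 24 = 168 h, exclusive (SAP Table 6.1: 1). Six active and two placebo subjects per dose group (Protocol 3.1.1).

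**Step 1: which sample is last in the SRD part?** Nominal EoT time = (day − 1) × 24 h. It is on treatment if below 168 h.

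| EoT day | Nominal time | On treatment? | Last value, most analytes | Last value, coagulation |
|---|---|---|---|---|
| 7 | 144 h | yes | 144 h | 144 h |
| 8 | 168 h | no | 96 h | 24 h |
| 9 | 192 h | no | 96 h | 24 h |
| 10 | 216 h | no | 96 h | 24 h |
| 11 | 240 h | no | 96 h | 24 h |

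On nominal times, 96 h is the last value on 4 of the 5 permitted EoT days. A Day 8 sample drawn before the dosing clock time would still fall inside the phase. For most analytes the table therefore uses one on-treatment sample and leaves out at least three. For coagulation it normally uses the 24 h sample and leaves out only the 4 h one.

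**Step 2: FE part, first period.** The period 2 pre-dose sample is taken 72 to 24 h before the second dose, so its time after the first dose is washout × 24 − (72, 48 or 24).

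- 7 days: 96, 120 or 144 h, all on treatment for period 1.
- 8 days: 120 or 144 h on treatment; 168 h not.
- 9 days: 144 h on treatment; 168 and 192 h not.
- 10 days: 168, 192 or 216 h, none on treatment.

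With a short washout, the sample drawn before the second dose can thus become the last on-treatment value for the first. The time point depends on scheduling.

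**Step 3: effect on the count.** The counts here are assumed for illustration. Let k of 6 active subjects be in range at baseline, out of range at 24 h and back in range at 96 h, with 96 h as the last value.

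| k | Planned table | Table of most extreme value |
|---|---|---|
| 1 | 0/6 | 1/6 = 16.7% |
| 2 | 0/6 | 2/6 = 33.3% |
| 4 | 0/6 | 4/6 = 66.7% |

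**Step 4: what the other displays give.**

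- By-time statistics include minimum and maximum (SAP 7), so an extreme value at 4, 24 or 48 h is visible. They do not count subjects or pair each with his baseline category.
- Listings highlight out-of-range values (Protocol 7.3.4). They are individual data, not frequencies by dose group.
- Adverse event (AE) tables count subjects, but for laboratory findings they depend on the investigator's judgement of relevance (SAP 7.8.2).

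None is a rule-based count of subjects out of range at any on-treatment time.

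**The case against.** Several objections are sound and limit the point.

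**It is not the only categorical laboratory display.** A reader might infer that it is. Clinically relevant findings become AEs and are counted by subject. Marked laboratory abnormalities form part of a separately tabulated class of other significant AEs. Hepatic injury is an adverse event of special interest (AESI) with numeric limits that apply at any sample (Protocol 5.2.6.1.4; SAP 7.8.1). This stands, but outside the numeric hepatic limits these tables rest on the judgement of an investigator who knows active from placebo (Protocol 4.1.5.1). Protocol 3.2 itself acknowledges possible observer bias for dose-dependent effects.

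**Transient values are not hidden from the report.** With six active subjects per group, by-time extremes and highlighted listings will reveal them. This stands. The shortfall is confined to the missing count.

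**The last value is not shown to be the least informative.** A reader might infer that it is, because 96 h is 96/3.3 = 29.1 predicted half-lives, or 96/26.5 = 3.6 at the longest half-life in Protocol Table 1.2.3: 1. The documents do not support that step. They say "human effective half-life of BI 764122 is predicted to be 3.3 h" but add that this may be substantially exceeded, and they give no time course for laboratory changes after a single dose. Protocol 1.3.2 describes a non-reversible ALT rise in dogs; a change that persists is what a late sample would catch.

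**Extreme-value tables have a cost.** Taking the extreme of several samples picks up more chance excursions than a single sample. In the FE fed arm the 4 h sample also follows a high-fat breakfast served 30 minutes before dosing. Both points stand and bear on how the added tables are read.

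**The sponsor's laboratory standard may already add displays.** SAP 7.8.2 cites it and it was not available for this review. The SAP text names no further shift table.

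**Conclusion.** The point holds as a limited reporting gap. The only reference-range shift table that SAP 7.8.2 specifies counts a resolved excursion as no shift, whatever the number of subjects affected. Abnormalities that persist to the last sample still appear in it. The affected samples are normally those at 4, 24 and 48 h, and only the 4 h sample for coagulation.

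A reader might infer that safety decisions are weakened. They are not: the primary endpoint is the percentage of subjects with drug-related AEs, and escalation rests on Safety Reviews of laboratory data to at least 48 h after dosing (Protocol 3.1.1), not on this end-of-trial table. The trial tests no hypotheses (Protocol 7.2).

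The conclusion assumes nominal sampling times and that the sponsor's standard adds no extreme-value shift table. It also relies on Table 5.2.3: 1 for the 24 h sample in both parts, because the SRD Flow Chart is not clearly legible there in the text available. The continuation of that table could not be read, so the timing statements cover only the analytes shown.

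**What to change.** In SAP 7.8.2, add two shift tables: baseline to the highest and baseline to the lowest on-treatment value relative to the reference range, taken across all on-treatment times. Present the SRD tables by dose group against pooled placebo (8 × 2 = 16 planned subjects), which gives a yardstick for chance excursions. Present the FE tables by fed and fasted state, with a note that the 4 h fed sample follows the high-fat meal. Keep the last-value table as supplementary.

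The cost is one table specification and its programming; no new samples or data are needed. If the cited sponsor standard already provides these tables, one sentence in 7.8.2 saying so is enough.
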